## 6. Research Plan

### 6.1 Design Overview

This is a pilot study of the efficacy of NIR stimulation for enhancing cognition and mood in older adults including those who are cognitively normal, those with mild cognitive impairment (amnestic and nonamnestic), and individuals with Parkinson disease. The overall hypothesis, drawn from previous literature, is that exposure to NIR stimulation will have positive effects on brain health and will result in better cognitive and mood performance. We propose to conduct a blinded parallel group sham controlled pilot trial, with half the participants in each group randomized to the real NIR treatment and half to the sham treatment condition. The two conditions are identical in all respects except that no near-infrared light stimulation will occur during the sham condition. The participants will consist of older adults recruited from the community, including The Village, and from UF and other clinics. The study will take place at the UF-VITAL lab located on The Village campus or in the Cognitive Neuroscience Laboratory at the Fixel Center for Neurologic Disease. The study design is shown below:

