## 6.2 Participants

Participants will include individuals, age 62 years and older, who are independently living and willing to undergo a two-week intervention program. Our study groups will consist of the following: 70 cognitively normal individuals (N= 35/group), 20 individuals with amnestic MCI (N=10/group), 20 individuals with nonamnestic MCI (N=10/group), and 40 nondemented individuals with Parkinson disease (N=20/group). Based on our previous intervention studies with older adults, we anticipate a 20% attrition rate and up to 50 screen failures. To account for screening failures and study attrition, we anticipate consenting 206 individuals.

**Informed Consent:** Informed consent will be obtained according to university and federal guidelines. The informed consent process may begin with the initial telephone screening call, when a prospective participant is contacted or calls to find out more information about the study (See Telephone Script). After that first phone contact, the participant will be sent a copy of the Informed Consent via hardmail or via email if they are interested, and/or scheduled for an appointment in the VITAL laboratory or at the Fixel Center for Neurologic Diseases to discuss the study in more detail and in person.

Other potential participants, particularly those seen during the clinics of the PI or co-investigators, will be directly asked about their interest in this study and will be provided a copy of the informed consent to review.

During the first study visit, the project will be explained in more detail to the potential participant by the study coordinator or approved staff and the Informed Consent will be reviewed. Participants will be informed that this is a randomized trial and that there is 50% likelihood they may receive the sham intervention. The participant will be given the opportunity to ask questions. No study interventions will begin until the Informed Consent

(ICF) paperwork is signed. Participant will be given a signed copy of the ICF paperwork, and a copy will be kept on file with the Principal Investigator.

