### **6.3 Recruitment**

Participants will be recruited from the Village and the community through advertisements, brochures, and flyers (See Appendix A). Targeted locations might include bulletin boards at community grocery stores, physician's offices, medical centers, retirement homes, etc. Occasionally, the project coordinator and investigators will make informational presentations about age-related changes in various community venues (e.g. health fairs, socials). As part of these presentations, we will encourage interested individuals to contact the VITAL lab to learn more ongoing research. Staff members of The Village who obtain signed permission from residents will forward resident names and contact information to the Study Coordinator.

Additional recruitment may occur through the clinics of the PI and co-investigators or other clinics at the Fixel Center (via flyers). These clinics focus on older adults including those with Parkinson disease, and potential participants will be directly asked about their interest in this study by their clinicians. Additionally, flyers will be distributed to other physicians at the Fixel Center.

Finally, recruitment may occur via IRB approved clinical and research databases. Thus, recruitment of normal older adults may take place via two IRB-approved research databases that are maintained by one of the co-investigators, [name]. These include the Claude D. Pepper Recruitment Registry (IRB #201601352, previously 415-2007) and the Participant Registry for Aging Research (IRB #201601448, previously 131-2002).

Recruitment of individuals with mild cognitive impairment or Parkinson disease may take place via INFORM (IRB #201501166, previously #416-2002), a clinical research database that is maintained by the Center for Movement Disorders and Neurorestoration (CMDNR). The INFORM database includes patients with both movement and cognitive disorders, including those who are seen in [name] and [name]'s Cognitive Disorders and Dementia clinics at the Fixel Center.

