#### 6.7.4 SHAM NIR Condition and Blinding

Participants in the sham control group will undergo identical procedures as the intervention group - screening, baseline testing, and LED cluster placement procedures. We have sham devices that look similar in all respects to the active devices, both transcranial and infranasal. The sham and active devices are coded and only one of the Investigators knows the code. The research assistant administering the stimulation sessions will not be aware of the participant's treatment status, and will have no role in post-intervention assessments. The research assistant administering post-intervention testing will be blinded to the treatment status of the participant.

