## 7.2. Randomization and Statistical Methods

**7.2.a. Randomization.** Participants in the Cognitively Normal, the MCI, and Parkinson groups will be independently assigned to Sham and Treatment groups on a 1:1 ratio. For the Cognitively Normal group, we anticipate an N of 35 in each treatment group. For each MCI group, we anticipate an N of 10 per treatment group. For the PD group, we anticipate an N of 20 per treatment group. Randomization will be stratified according to age and MoCA/MMSE scores so as to prevent different average ages or cognitive status scores between the treatment groups. Treatment assignment will be pseudorandomized in order to have comparable distributions of age and cognitive screening scores across Sham and Treatment interventions. Procedures will be followed so that group assignments are not available to individuals administering and scoring baseline/pre-intervention and post-intervention cognitive/mood data.

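### Section 7.2.a describes assignment both as stratified randomisation and as pseudorandomisation for balance, with no stated random element for the latter and no concealment of the next allocation from recruiters, screeners or the code-holder

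*Protocol*

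**What the plan says.** Section 6.1 presents a blinded, sham-controlled, parallel-group trial "with half the participants in each group randomized to the real NIR treatment and half to the sham treatment condition". Section 7.2.a says participants in each diagnostic cohort "will be independently assigned to Sham and Treatment groups on a 1:1 ratio". It then gives two accounts of how this is done. The first is a stratified draw: "Randomization will be stratified according to age and MoCA/MMSE scores so as to prevent different average ages or cognitive status scores between the treatment groups". The second comes straight after it, makes no mention of strata and uses a different term for the procedure: "Treatment assignment will be pseudorandomized in order to have comparable distributions of age and cognitive screening scores across Sham and Treatment interventions".

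On who is kept from the assignments, section 7.2.a says: "Procedures will be followed so that group assignments are not available to individuals administering and scoring baseline/pre-intervention and post-intervention cognitive/mood data". Section 6.7.4 adds: "The sham and active devices are coded and only one of the Investigators knows the code". It also says that the assistants who run the stimulation sessions and the post-intervention testing are unaware of treatment status.

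On entry to the trial, section 6.3 says: "Additional recruitment may occur through the clinics of the PI and co-investigators". Section 6.5 has the project coordinator do the screening. Section 11 has a co-investigator and/or research assistants coordinate recruitment and screening. The cohorts are small (section 6.2): "70 cognitively normal individuals (N= 35/group), 20 individuals with amnestic MCI (N=10/group), 20 individuals with nonamnestic MCI (N=10/group), and 40 nondemented individuals with Parkinson disease".

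**The concern.** A random draw within strata and an assignment steered so that the arms come out alike are different procedures. In the second, a participant's age, score and the earlier assignments may settle the arm, and the protocol does not say that chance keeps a part.

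If the next arm can be foreseen, the decision to approach or enrol someone, or when to do so, can depend on it. Balance on age and screening score does not protect against selection on anything else, such as motivation or expectation of benefit. The Group by Occasion ANOVAs in section 7.3 rely on fair assignment and are run separately in each cohort. In a cohort of 20, a few steered entries could matter. Analysis cannot repair this after enrolment.

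**Working it through.** **1. The texts side by side.** The arm sizes agree between sections 6.2 and 7.2.a: 35 + 35 = 70, 10 + 10 = 20 (twice) and 20 + 20 = 40. The method does not agree. One sentence names stratified randomisation, and the next names pseudorandomisation for comparability and does not define it.

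**2. Who is covered.** Named as not knowing the assignment: those who test and score before and after treatment, and the session operator. Not named: recruiting clinicians, the screening coordinator and whoever makes the assignment. One investigator holds the device code. Investigators' clinics recruit, and a co-investigator may coordinate recruitment and screening. Nothing says these are different people.

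**3. The stratifier.** Section 7.2.a names MoCA/MMSE. Sections 6.4b and 6.5 and Tables 1 and 2 use the MoCA or the DRS-2 (or DRS), and the MMSE is in neither table. For a participant screened with the DRS-2, the stated stratifying score may not exist.

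**4. How foreseeable allocation would be.** The protocol gives no figure to reproduce and no rule, cut-points or block size, so these are assumptions. Cohorts of 70, 40 and 20 were simulated with two balancing factors of two levels each (2x2) or three levels each (3x3), all levels equally likely. There were 3,000 runs per setting (500 for simple randomisation). The guesser is assumed to know the method, all past assignments by arm, and the next participant's strata.

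Let p be the probability of active treatment given the history. The best guess is right with probability max(p, 1 - p), and the allocation is certain if p is 0 or 1. Both are averaged over participants.

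- Blocks of size b within strata: p = (b/2 - active so far in block) / (b - all so far in block).
- Balancing: d is active minus sham in the participant's age level, plus the same in the score level. If d = 0, p = 0.5. Otherwise the under-represented arm is chosen with probability 1 (deterministic), 0.8 or 0.7.

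| Method | Certain | Guessed correctly |
|---|---|---|
| Simple randomisation | 0% | 50% |
| Blocks of 6 in strata | 3-22% | 57-67% |
| Blocks of 4 in strata | 14-31% | 62-70% |
| Balancing, probability 0.7 | 0% | 65-67% |
| Balancing, probability 0.8 | 0% | 72-74% |
| Deterministic balancing | 66-72% | 83-86% |

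Two checks:

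- Under deterministic balancing each allocation is either certain or a fair coin, so the guess rate is 0.5 + 0.5 x certain share. The extremes give 0.5 + 0.5 x 0.717 = 0.859 and 0.5 + 0.5 x 0.661 = 0.831, which match the simulated 0.858 and 0.831.
- For a complete block of 4 the exact guess rate is (1/2 + 2/3 + 2/3 + 1)/4 = 0.708. The simulated values lie just below because some blocks are left unfinished.

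In participants, deterministic balancing makes 0.661 to 0.690 x 20 = 13 to 14 allocations certain in each MCI cohort, and 0.699 to 0.717 x 70 = 49 to 50 in the cognitively normal cohort. If the rule also balances arm totals, a separate simulation with two binary factors gives 78-80% certain and 89-90% guessed.

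**5. Strata in the MCI cohorts.** With 20 people, a 2x2 layout leaves 20/4 = 5 per cell and a 3x3 layout 20/9 = 2.2. Many strata would leave most blocks incomplete and lose the balance they were meant to give.

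**The case against.** The strongest defence is that the two sentences share one aim and may describe one constrained scheme twice. The word *pseudorandomized* does not mean deterministic. A pre-generated stratified list, or a minimisation program, needs no person to see the running allocation. Section 6.6 randomises only those who meet the criteria, and many criteria are test cut-offs. Coded devices that look alike mean that staff who track past codes would not know which code is active. Block sizes and sequence generation are commonly left to another document.

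Most of this stands. A reader might infer that participants are not drawn at random, or that the person assigning can foresee most allocations. The documents do not support either as a fact: the same paragraph says stratified randomisation, no passage says a person chooses the arm, and the high figures need both a deterministic rule and a guesser who knows the arms. An unstated block size would be no finding.

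Two things remain. The protocol itself contains a sentence that permits a weaker rule, and a separate randomisation plan would have to contradict that sentence to cure it. And device coding is blinding after assignment. It limits who could exploit predictability, but the code-holder is an investigator whose part in enrolment or assignment is not stated.

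**Conclusion.** The point holds as an unresolved and badly fixed assignment rule, not as proof that the trial is not randomised. Section 7.2.a gives two descriptions, states no random element for one, and extends its safeguard to testers and scorers but not to those who recruit, screen or hold the code.

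The size is conditional. If balancing is deterministic or done by hand, about two thirds or more of allocations would be foreseeable to someone who knows the past assignments and the active code. With a random element none would be certain, and with stratified blocks of 4 or 6 at most about three in ten. These figures rest on assumed strata and rules. The correction is cheap and should be made before enrolment.

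**What to change.** Delete the sentence on pseudorandomisation and state one method:

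- A computer-generated list with permuted blocks of randomly varying size within each cohort, stratified by age and by a single screening score that is actually collected in that cohort. Use few strata in the two MCI cohorts of 20.
- The data management group described in section 11 generates and holds the list. A coded device is released only after eligibility is confirmed and the participant is enrolled.
- The code-holder in section 6.7.4 takes no part in recruitment, eligibility decisions or assignment. The release step must be reconciled with that section, for example by writing the list in device codes so that the key stays with the code-holder.

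Minimisation with a random element would also remove certain allocations. At probability 0.8, however, it is 72-74% guessable against 62-70% for blocks of 4, so it offers no clear gain in concealment.

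The cost is one paragraph, a list from an existing group, and slightly less exact balance on age and screening score. The last can be offset by adding both as covariates to the section 7.3 analyses. The planned 2x2 ANOVA includes neither: age appears only in the additional predictor and moderator analyses, and the screening score in none.

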## 7.2.b. Missingness and Intent to Treat.

All data will be checked for missingness, out-of-range values, and distributional form (i.e., normality, homogeneity of variance). Decisions regarding use of parametric vs. nonparametric statistics will be based on the results of those analyses. Standard summary statistics will be provided for pre- and post-stimulation. Intent to treat analysis will be used to reduce selective attrition bias; participants who are unwilling/unable to continue with intervention will be encouraged to attend the post intervention testing, if possible. Thus, statistical analyses will be performed on two data sets: 1) on all subjects who were successfully screened, randomized and able to participate in at least 1 week of the assigned intervention, regardless of study

completion (intention-to-treat analysis); and 2) on subjects who were successfully screened, randomized and able to complete at least 80% of the treatment assignment.

### **7.3. Statistical Analyses**

Data for each group (Cognitively Normal, MCI, Parkinson) will be analyzed separately. However the same analytic approach will be taken for each, as described below. Some analyses will be truncated for the MCI groups due to the smaller sample size.

*Aim 1:* Aim1 will test the hypothesis that individuals in the active stimulation group will show improved cognitive function compared to the sham group. Separate mixed model ANOVAs (2 [Group: Active Stimulation, Sham stimulation] x 2 [Occasion: Pre-testing, Post-testing]) will be conducted using the executive and Memory outcome variables. When significant, appropriate post-hoc analyses will be conducted. Additional analytic techniques will involve 'change score' analyses, as well as analyses examining predictors of changes (i.e., age, education, gender).

*Aim 2:* Aim 2 will test the hypothesis that individuals in the active stimulation group will show improved emotion/psychological function compared to the sham group. Separate mixed model ANOVAs (2 [Group: Active Stimulation, Sham stimulation] x 2 [Occasion: Pre-testing, Post-testing]) will be conducted using the mood outcome variables (mood modules NIH Toolbox, STAI, POMS, BDI-II). When significant, appropriate post-hoc analyses will be conducted. Additional analytic techniques will involve 'change score' analyses, as well as analyses examining predictors of changes (i.e., age, education, gender).

*Aim 3:* This neuroimaging aim is exploratory and will test the hypothesis NIR intervention will produce pre-post increases in frontal and temporal brain markers of MRS ATP function and pre-post increases in connectivity in frontal and medial temporal lobe mediated resting state brain networks (resting state fMRI). Although this aim will require extensive data reduction, the overall data analytic plan is similar to that of Aims 1 and 2.

*Aim 4:* This is aim is specific to Parkinson disease and will test the hypothesis that active NIR stimulation will result in greater pre-post intervention improvement in motor parameters (UPDRS, fine motor speed, gait, balance) than sham. Separate mixed model ANOVA's will be conducted similar to those described in Aims 1 and 2.

Finally, we plan to examine whether various 'factors' might potentially be moderators or mediators to intervention success. WE plan to examine age, education, gender, health comorbidities, processing speed and mood.

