## 6.6 Pre and Post-Intervention Measures

Participants who meet study criteria and who remain interested in participating in the 2 week intervention will be randomized to treatment or sham groups and undergo a baseline/ pre-intervention testing. The pre-intervention measures will be administered by a trained psychometrist or research assistant who will be blinded to group assignment (sham, real NIR stimulation).

The pre-intervention testing will take approximately 3 – 3.5 hours, and will consist of measures of executive function, recent memory, and mood. These same measures will be given after the two-week intervention has completed.

Individuals with Parkinson disease will complete the pre and post intervention visits when they are “off” their typical dopaminergic medications. This is identical to what Parkinson patients are asked to do as part of standard clinical care when seen at the UF Movement Disorders Clinic. To do so, the Parkinson patients will refrain from taking their parkinsonian medications overnight, with no dopa medication after 10:00 PM the night before. The theoretical rationale for evaluating patients when off dopamine medication is to obtain an index of the true status of their disease state.. The remainder of the protocol (i.e., screening, intervention) will be completed when participants are on their normal medications. When tested ‘off medication’, patients may experience increased slowness, tremors and stability. Because of this, they will be closely monitored and provided a wheel chair. If they become too uncomfortable they can take their medication and will be withdrawn from the study.

In previous IRB- approved studies, we have tested Parkinson patients off medication while they completed an array of cognitive, EEG, and other tasks. We have found that the tolerability was quite good and no participants dropped out of the study for the medication issue. In the current study, we are implementing testing ‘off dopa’ medications at the recommendation of the Parkinson Foundation.

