
**6.6.4b. Description of State Trait Anxiety Inventory** (STAI; Spielberger, 1983a; 1983b; 1989). The STAI is a 40-item questionnaire that is used to assess current (state) and general (trait) levels of anxiety. Higher scores represent higher levels of anxiety, or feelings of worry, tensions, and stress. Items on the questionnaire include ratings of statements such as "I feel calm", "I am jittery", and "I feel nervous". The STAI has been used extensively in clinical and research settings and displays a test-retest reliability of 0.31 to 0.86 and internal consistency alpha coefficients of 0.86 to 0.95 (Spielberger et al., 1983a). Further, this measure shows high convergent validity with other measures of anxiety (0.72 to 0.86; Spielberger et al. 1989).

**6.6.4c. Description of Profile of Mood States, short form** (POMS, Curran et al., 1995). This is a 30 item self- report questionnaire of mood states such as "discouraged", "grouchy", "vigorous", and "efficient". The short form version of the POMS is easy to administer, and yields information about transient current mood states. The measure is grouped into subscales including tension, depression, anger, fatigue, and vigor. Test-retest reliability ranges from 0.65 to 0.74, internal consistency is 0.93, and the test also features high degrees of construct validity (Curran et al., 1995).

**6.6.4d. Description of Beck Depression Inventory-II** (BDI-II; Beck et al., 1996). This is a 21 item self-report questionnaire of symptoms of depression such as sadness, self-criticalness, loss of interest, or somatic changes such as insomnia or increased sleep, increased or decreased appetite, and low energy. This questionnaire allows one to characterize levels of depression as mild, moderate, or severe, depending on the total score. The BDI-II has strong convergent validity, internal consistency ( $\alpha=.91$ ) and test-retest reliability ( $r=.93$ ) and has been used extensively in clinical and psychological research.

**6.6.4f. Description of Apathy Scale** (AS, Marin et al., 1991). This is a 14 item self-report questionnaire that assesses for symptoms of motivation, drive, and initiative. Participants answer questions on a 5 point likert scale ranging from 0 to 4. The AS has been subgrouped into components reflecting cognitive, affective, and behavioral components of apathy. Test-retest reliability is strong, and the AS has strong convergent validity with real world indicators of behavior (Ferencz et al., 2012).

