## **6.7 Near-infrared (NIR) Stimulation Protocol**

**Overview:** Participants in both the real and sham conditions will participate in a total of six intervention sessions, 3 sessions a week, over a two-week period. Each session will include 40

minutes of “stimulation” time, followed by completion of a brief adverse events questionnaire and a brief mood questionnaire (POMS). Total session time in the lab may take up to 1.5 hours. During each session, the participant will be seated comfortably in a chair. Clusters of LED’s will be positioned across various regions of the scalp via a flexible head cap. Onset of the NIR light stimulation will be controlled by a MedX Console unit. During the 40 minutes of NIR stimulation or sham stimulation, the participants will view nature documentaries (BBC Life documentary series; Gunton, 2009) that are presented during the period of stimulation. This is being done in order to standardize cognitive engagement and control for differences in cognitive activity during stimulation.

In addition to stimulation in the laboratory, participants may be asked to do daily intranasal stimulation in their home. They will be provided Vielight intranasal devices (described below) and asked to stimulate themselves for 25 minute sessions on the days they do not come to the lab (i.e., 2 days during week 1 and 2 days during week 2).

[figure not shown]

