#### Equipment Sterilization

Following each session, the 6 MedX LED clusters and 2 Vielight intranasal leads will be sterilized with disinfectant wipes (PDI Super Sani-Cloth Germicidal Disposable Wipes) before storage. The manufacturer's recommendations are to clean equipment with sterilizing swabs in between sessions. In addition, a new flexible net caps will be used for each participant.

**Questionnaires:** Following the 40-minute stimulation period all participants will fill out the POMS short form and will be queried for adverse events (using the Adverse Events log). Completion of these questionnaires will take place at the end of each session.

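### POMS is scored after all six sessions, but the stated analysis uses only the pre and post scores; a baseline-adjusted longitudinal model would use the rest at no extra data cost

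*Protocol*

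**What the plan says.** **Collection.** Section 6.7 plans "six intervention sessions, 3 sessions a week, over a two-week period". The questionnaires paragraph at the end of Section 6.7.3 says "Following the 40-minute stimulation period all participants will fill out the POMS short form", and on timing, "Completion of these questionnaires will take place at the end of each session". POMS also belongs to the baseline battery, and Section 6.6 says of that battery: "These same measures will be given after the two-week intervention has completed". Table 2 agrees, marking POMS at baseline, intervention and follow-up.

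**Outcome definition.** Section 7.1 lists POMS among the secondary Aim 2 outcomes and defines it as pre-to-post change. The Aim 2 co-primary outcomes are two NIH Toolbox emotion scales, which are collected only before and after the intervention.

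**Analysis.** For Aim 2, Section 7.3 states that mixed ANOVAs "will be conducted using the mood outcome variables (mood modules NIH Toolbox, STAI, POMS, BDI-II"), with the within-person factor given as "2 [Occasion: Pre-testing, Post-testing". It adds change-score analyses and predictors of change. No analysis of the in-session scores is named. Diagnostic groups are analysed separately.

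**Reliability.** Section 6.6.4c says of POMS: "Test-retest reliability ranges from 0.65 to 0.74".

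**Analysis set.** Section 7.2.b defines the intention-to-treat set as those randomised who took part in at least one week of intervention, whether or not they completed the study.

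**The concern.** The protocol is not silent on POMS. It names the scale in Section 7.3 and gives it the same two-occasion design as the STAI and BDI-II, which really are collected only twice. POMS is collected eight times, and the six session scores have no stated role.

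Three things are at stake:

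- **Precision.** POMS measures short-lived mood, and one score after treatment is noisy. The groups analysed separately are small: 35, 20 and 10 per arm.
- **Incomplete follow-up.** Section 6.2 expects 20% attrition. At three sessions a week, someone who completes one week would usually have about three POMS scores after randomisation. Without a post-test that person is in the intention-to-treat set but contributes nothing to a pre-post contrast.
- **Time course.** Section 6.7.2 describes a brief study meant to gauge effect sizes and feasibility. POMS is the only mood scale that could show whether a change appears early or builds up over the sessions.

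**Working it through.** The protocol gives no power or precision figure for POMS, so there is none to reproduce.

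**Step 1. How much is unused.**

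- POMS occasions: 1 baseline + 6 sessions + 1 follow-up = 8. The ANOVA uses 2, so 6/8 = 75% are unused.
- Mood instruments in Section 6.6.4: five (Toolbox Emotion, STAI, POMS, BDI-II, Apathy Scale). Administrations: 5 × 2 + 6 = 16, so 6/16 = 37.5% are unused.
- By items: Toolbox 76 + 89 + 26 + 20 = 211; STAI 40, BDI-II 21, Apathy Scale 14, POMS 30. Pre plus post is 2 × (211 + 40 + 21 + 14 + 30) = 632. In-session POMS is 6 × 30 = 180. Unused: 180/812 = 22%.

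**Step 2. Residual variance per person** (score variance = 1). With two occasions, the arm-by-occasion interaction test is the same test as comparing change scores between arms. Assume an equal correlation r between all occasions, using the protocol's retest range of 0.65 to 0.74. With m post-baseline scores:

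- change from baseline: (1 − r)(1 + 1/m)
- mean of post-baseline scores, adjusted for baseline: (1 + (m − 1)r)/m − r²

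| Analysis | r = 0.65 | r = 0.74 |
|---|---|---|
| Pre-post change (stated), 2(1 − r) | 0.70 | 0.52 |
| Follow-up adjusted for baseline, 1 − r² | 0.578 | 0.452 |
| Mean of seven, change from baseline, (1 − r) × 8/7 | 0.40 | 0.297 |
| Mean of seven, adjusted for baseline, (1 + 6r)/7 − r² | 0.278 | 0.230 |

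The two sources of gain, kept apart:

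- Baseline adjustment alone: 0.578/0.70 = 0.83 and 0.452/0.52 = 0.87, so 17% and 13% lower.
- The extra scores alone: 0.278/0.578 = 0.48 and 0.230/0.452 = 0.51, so 52% and 49% lower. For change scores, (8/7)/2 = 0.571, so 43% lower whatever r is.

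**Step 3. On the effect scale.** Smallest detectable effect = (1.96 + 0.842) × √(2 × variance / n per arm), assuming two-sided alpha 0.05 and 80% power. Entries run from r = 0.65 to r = 0.74, in SD units.

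| n per arm | Pre-post change | Follow-up, baseline-adjusted | Mean of seven, baseline-adjusted |
|---|---|---|---|
| 35 | 0.56–0.48 | 0.51–0.45 | 0.35–0.32 |
| 20 | 0.74–0.64 | 0.67–0.60 | 0.47–0.42 |
| 10 | 1.05–0.90 | 0.95–0.84 | 0.66–0.60 |

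The last column holds only if the effect is the same on all seven occasions.

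**Step 4. If the effect builds up.** Suppose it grows in equal steps to 0.5 SD at follow-up (an assumed size). The seven-occasion average effect is 0.5 × (1 + 2 + … + 7)/49 = 0.5 × 28/49 = 0.29 SD. At 35 per arm, using change scores, power for the average is 0.47–0.59. For the pre-post contrast it is 0.71–0.83. Averaging then loses power.

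**The case against.** **The stated test matches the stated outcome.** Section 7.1 defines POMS as pre-post change and Section 7.3 tests that. This stands: there is no contradiction and no invalid test. The point concerns efficiency and unused information on a secondary scale. A session-level analysis may also sit in a statistical analysis plan that is not shown. Even so, the protocol itself fixes two occasions for POMS, so this is more than detail left for later.

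**Session scores are not repeats of the endpoint.** They are taken straight after stimulation, whereas follow-up is a separate visit. In the Parkinson group (40 of 150 planned participants), Section 6.6 has sessions on usual medication and the baseline and post visits off it. This also stands. Comparison of the randomised arms at each session remains valid, but pooling session and follow-up scores would mix two questions, and the equal-correlation assumption is weakest in this group.

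**Stronger readings that the protocol does not support.**

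- A reader might infer that most of the mood data are lost. That is true of POMS only; across all mood instruments the share is 37.5% of administrations or 22% of items.
- A reader might infer that the session scores will be discarded. The protocol says no such thing; it only names no analysis for them.
- A reader might credit the repeated scores with the whole drop from 0.52–0.70 to 0.23–0.28, which is 56–60%. Part of that is baseline adjustment, which needs no session data.
- A reader might expect the follow-up estimate itself to become much more precise. With separate arm effects at each occasion and complete data, session scores add essentially nothing to that estimate. They help through participants whose follow-up is missing.

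**Conclusion.** The point holds as a low-priority improvement. Six of eight POMS scores enter no stated analysis, and intention-to-treat participants without a post-test drop out of the POMS contrast. No co-primary outcome is affected.

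The dependable gain is a 13–17% lower residual variance from baseline adjustment, plus the information recovered from people with session scores but no post-test. That second part cannot be sized: the protocol expects 20% attrition but not how many of those people would finish a week, and it encourages those who stop to attend post-testing.

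The further 49–52% from averaging all seven scores is an upper illustration. It needs equal correlation of 0.65–0.74 between all occasions, although the protocol gives no interval for its retest figures, and a similar effect on every occasion. Under an effect that builds up, the average can be worse than pre-post.

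**What to change.** In Section 7.3, Aim 2, give POMS its own analysis, run separately within each diagnostic group:

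1. Fit a repeated-measures mixed model to all post-baseline POMS scores, adjusted for baseline, with arm, occasion (six sessions and follow-up) and arm-by-occasion terms.
2. Keep the arm difference at follow-up as the main POMS estimate, taken from this model with a 95% interval.
3. Report the arm difference averaged over the six sessions separately, as a supplementary on-treatment effect with a 95% interval. Show the session-by-session differences for the time course.
4. Do not pool session and follow-up scores into one average, above all in the Parkinson group, where the medication state differs between them.
5. Fix a simple covariance structure in advance for the smallest groups. A fully general one for seven occasions has 7 × 8/2 = 28 parameters, too many for 10 per arm.

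**Cost.** Slightly more analysis work; no new data, visits or participant burden. The session average answers a different question (mood just after stimulation) and should be labelled so. The model relies on missing follow-up scores being predictable from the scores observed, which should be stated.
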